## 9. Subgroup analysis

The analysis of all endpoints will be done for all patients of both countries as sample size did not take into consideration country-specific analyses of the specified primary endpoint. Thus, we will merge the data from the four sites we will analyse the resulting database as unique source of data.

However, a subgroup analysis of the primary endpoint and main secondary endpoint (mortality at month 2) will be done by study site (Mozambique and Tanzania, CD4 counts and viral load).

A separate analysis of the primary and secondary endpoints will also be performed by sex of participants, in order to assess if differences arise in any of the outcomes.

## 10. Other Analyses

We will do a comparison of baseline characteristics between participants who can complete the study and participants who we will lose during their follow-up period. We will do this analysis to test if the participant loss is by chance. We will use Chi statistical test. The variables that we will test are: Country (COUNTRY), Sex (SEX), Ethnic group (ETHNIC), Level of education (EDUCATION), Employment Status (EMPLOYMENT), Early HIV positive result (EARLY\_HIV), Current taking antiretroviral (ART\_YN), Previous TB episodes (TB\_TX\_YN), Received BCG vaccination (BCG\_YN), Participant live alone? (ALONE), Patient taking cotrimoxazole (CTX\_YN), Karnofsky Performance Status Scale (KARNOFSKY), Patient's WHO clinical Stage (WHO\_STAGES) and TB treatment start (TB\_TX\_START\_YN).

## 11 Reporting Conventions

We will use two decimals in numeric results. We will round to up the value of second decimal when the third decimal value will be equal or higher than 5, in other cases we will do nothing.

All confidence intervals (CI) will be calculated at 95% of confidence. These will be calculated using the logit-transformed confidence interval method. We will use the Haybittle-Peto approach for the evaluation of the p-value, under this approach we will consider statistically significant when the p-value's test is lower than 0.05 in the final analysis

Where necessary, variables will be categorized using the cut-off described in previous works and research publish documents. For example, CD4 counts will be categorized in 3: less than 100 CD4 counts per ml (as in STAMP trial), 100-200 CD4 counts per ml, and above 200.

However, depending on the frequencies observed, these categories could be refined. When we don't have a reference cut-off value for a continuous variable, we will calculate these values using the terciles, quartiles or quintiles of the variable and cut it using this calculated cut-off values. (For example, if we want to divide the participants age in three categories, we will calculate the terciles values and later we calculate a new categorical variable using these points. Then we will have a new age group with three categories: from minimum value to first tercile, from first to second tercile and finally from second tercile to maximum value).

## 12 Technical Details

The statistical analysis we will performed with the Stata software. We will use the Stata 17 version or the most up to date available version when analysis takes place. Scripts used in the analysis can be published as supplementary material of the main publication or uploaded into a public repository.

## 13 Listing of Tables, Listings and Figures

We will show the results using Tables and Figures. The following is a description of these tables. Some of these tables will summarize the results for ITT and per protocol analysis and always we will make it by study arm. According to the figures we will draw the Kaplan-Meier curves to show the proportion of participants initiating TB treatment over time, stratified by lab confirmation, CD4 count category, viral load and country. Venn diagrams showing the distribution of participants starting TB treatment by positivity to each test will be displayed.

Table 1. Baseline Characteristics of participants by study arm for ITT and per protocol analysis

	ITT Analysis		Per Protocol Analysis	
	Standard-of-care group (n=XXXX)	Intervention group (n=XXXX)	Standard-of-care group (n=XXXX)	Intervention group (n=XXXX)
Age (years)	XX.X (XX.X)	XX.X (XX.X)	XX.X (XX.X)	XX.X (XX.X)
Gender	XXX (XX%)	XXX (XX%)	XXX (XX%)	XXX (XX%)
Country Site				
Mozambique	XXX (XX%)	XXX (XX%)	XXX (XX%)	XXX (XX%)

Tanzania	XXX (XX%)	XXX (XX%)	XXX (XX%)	XXX (XX%)
Employment Status				
Employed	XXX (XX%)	XXX (XX%)	XXX (XX%)	XXX (XX%)
Unemployed	XXX (XX%)	XXX (XX%)	XXX (XX%)	XXX (XX%)
Unable to work	XXX (XX%)	XXX (XX%)	XXX (XX%)	XXX (XX%)
Student	XXX (XX%)	XXX (XX%)	XXX (XX%)	XXX (XX%)
House man/wife	XXX (XX%)	XXX (XX%)	XXX (XX%)	XXX (XX%)
Retired	XXX (XX%)	XXX (XX%)	XXX (XX%)	XXX (XX%)
Other	XXX (XX%)	XXX (XX%)	XXX (XX%)	XXX (XX%)
Previous TB episodes				
Yes	XXX (XX%)	XXX (XX%)	XXX (XX%)	XXX (XX%)
No	XXX (XX%)	XXX (XX%)	XXX (XX%)	XXX (XX%)
BCG vaccination				
Yes	XXX (XX%)	XXX (XX%)	XXX (XX%)	XXX (XX%)
No	XXX (XX%)	XXX (XX%)	XXX (XX%)	XXX (XX%)
Unknown	XXX (XX%)	XXX (XX%)	XXX (XX%)	XXX (XX%)
Cotrimoxazol treatment				
Yes	XXX (XX%)	XXX (XX%)	XXX (XX%)	XXX (XX%)
No	XXX (XX%)	XXX (XX%)	XXX (XX%)	XXX (XX%)
Unknown	XXX (XX%)	XXX (XX%)	XXX (XX%)	XXX (XX%)
Antiretroviral treatment				
Yes	XXX (XX%)	XXX (XX%)	XXX (XX%)	XXX (XX%)
No	XXX (XX%)	XXX (XX%)	XXX (XX%)	XXX (XX%)
Unknown	XXX (XX%)	XXX (XX%)	XXX (XX%)	XXX (XX%)
CD4 count <200cells/mm 				
Yes	XXX (XX%)	XXX (XX%)	XXX (XX%)	XXX (XX%)

No	XXX (XX%)	XXX (XX%)	XXX (XX%)	XXX (XX%)
Who clinical stage				
Stage I	XXX (XX%)	XXX (XX%)	XXX (XX%)	XXX (XX%)
Stage II	XXX (XX%)	XXX (XX%)	XXX (XX%)	XXX (XX%)
Stage III	XXX (XX%)	XXX (XX%)	XXX (XX%)	XXX (XX%)
Stage IV	XXX (XX%)	XXX (XX%)	XXX (XX%)	XXX (XX%)

Table 2. Microbiological results by study arm for both the ITT and per protocol analyses

	ITT Analysis			Per Protocol Analysis		
	Standard-of-care group (n=XXXX)	Intervention group (n=XXXX)	p-value	Standard-of-care group (n=XXXX)	Intervention group (n=XXXX)	p-value
Samples available	XXX (XX.X)	XX.X (XX.X)	X.XXX	XX.X (XX.X)	XX.X (XX.X)	X.XXX
Sputum Ultra available	XXX (XX%)	XXX (XX%)	X.XXX	XXX (XX%)	XXX (XX%)	X.XXX
Sputum Ultra results						
Negative	XXX (XX%)	XXX (XX%)	X.XXX	XXX (XX%)	XXX (XX%)	X.XXX
Indeterminate	XXX (XX%)	XXX (XX%)		XXX (XX%)	XXX (XX%)	
Positive	XXX (XX%)	XXX (XX%)		XXX (XX%)	XXX (XX%)	
Urine Ultra available		XXX (XX%)			XXX (XX%)	
Urine Ultra results						
Negative		XXX (XX%)			XXX (XX%)	
Indeterminate		XXX (XX%)			XXX (XX%)	

Positive		XXX (XX%)			XXX (XX%)	
Stool Ultra available		XXX (XX%)			XXX (XX%)	
Stool Ultra results						
Negative		XXX (XX%)			XXX (XX%)	
Indeterminate		XXX (XX%)			XXX (XX%)	
Positive		XXX (XX%)			XXX (XX%)	
AlereLAM available	XXX (XX%)			XXX (XX%)		
AlereLAM results						
Negative	XXX (XX%)			XXX (XX%)	XXX (XX%)	
Indeterminate	XXX (XX%)			XXX (XX%)	XXX (XX%)	
Positive	XXX (XX%)			XXX (XX%)	XXX (XX%)	
Microbiologically confirmed	XXX (XX.X)	XX.X (XX.X)	X.XXX	XX.X (XX.X)	XX.X (XX.X)	X.XXX

Table 3. TB treatment initiation within 72 hours

	ITT Analysis			Per Protocol Analysis		
	Standard-of-care group (n=XXXX)	Intervention group (n=XXXX)	p-value	Standard-of-care group (n=XXXX)	Intervention group (n=XXXX)	p-value
Start treatment within 72 hours	XXX (XX.X%)	XXX (XX.X%)	X.XXX	XXX (XX.X%)	XXX (XX.X%)	X.XXX
Hours to start treatment (treatments <= 72h)	XXX (XX%)	XXX (XX%)	X.XXX	XXX (XX%)	XXX (XX%)	X.XXX

Days to start treatment (treatments > 72h)	XXX (XX%)	XXX (XX%)	X.XXX	XXX (XX%)	XXX (XX%)	X.XXX
Start treatment within 72 hours						
Confirmed TB	XXX (XX%)	XXX (XX%)	X.XXX	XXX (XX%)	XXX (XX%)	X.XXX
Unconfirmed TB	XXX (XX%)	XXX (XX%)	X.XXX	XXX (XX%)	XXX (XX%)	X.XXX

Table 4 TB outcomes at 8 weeks by arm (ITT analysis)

	Standard-of-care group (n=XXXX, %)	Intervention group (n=XXXX, %)	Risk Difference % (95% CI)	p-value
Start treatment within 72 hours	XXX (XX.X)	XX.X (XX.X)	X.X (X.X, X.X)	X.XXX
Microbiologically confirmed TB	XXX (XX%)	XXX (XX%)	X.X (X.X, X.X)	X.XXX
Clinically diagnosed TB	XXX (XX%)	XXX (XX%)	X.X (X.X, X.X)	X.XXX
Deaths at week 8	XXX (XX%)	XXX (XX%)	X.X (X.X, X.X)	X.XXX

Figure 1. Trial flowchart

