| TB Investigations | | Sputum Ultra | | | | | |
| | Urine | Stool | | | | | |
| | AlereLAM# | Ultra | | | | | |
| | Sputum Ultra* | Urine Ultra | | | | | |
| Samples collected and tests | Blood CD4 | Urine AlereLAM | | | | | |
| | | 2x Oral Swabs | | | | | |
| | | Urine FujiLAM | | | | | |
| | | Blood CD4 | | | | | |
| | | Blood for CRP | | | | | |
| Results issued | | | | X | | | |
| Further contacts | | | | | | | |
| Verification TB diagnosis / ad hoc TB investigations | | | | X | X | X | X |
| Verification TB treatment initiation | | | | X | X | X | X |
| Verification vital status | | | | X | X | X | X |
| HIV care / ART | | | | X | X | X | X |

*Sputum Ultra whenever the patient has cough, fever, weight loss or night sweats and/or Ultra on any tissue (including lymph nodes) from patients with suspected extrapulmonary TB

#Urine LAM if patients have currently signs and symptoms of TB (pulmonary and/or extrapulmonary), or with advanced HIV disease (1) or who are seriously ill (2) or else irrespective of signs and symptoms of TB and with a CD4 cell count of less than 200 cells/mm³.

[&]CD4 count testing will be done if not available within the last 3 months. Most recent viral load will be captured (if available)

**urine should be collected in all participants in the control arm, irrespective of whether LAM test is done.

This project is part of the EDCTP2 programme supported by the European Union

12. Laboratory procedures and storage of samples

Samples will be processed and results issued back to attending physicians as soon as possible. AlereLAM results should be available within two hours from specimen collection. Ultra results should be provided within 24 hours from being collected at the participating hospital laboratory associated facilities.

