13.2.2 Statistical methods

Variables will be summarized using descriptive statistical methods. Continuous data will be described using the mean and standard deviation statistics when these values follow the normal distribution. Otherwise we will use the median and interquartile range when we will not assume this distribution. Categorical values will be summarized using frequency and/or percentages.

For categorical comparisons we will use a Chi-square test or Fisher exact test according to the

This project is part of the EDCTP2 programme supported by the European Union

data characteristics. Likewise, the continuous comparisons will be tested by Student t-test, Anova test or Kruskal Wallis test.

When necessary, we will transform the continuous data, especially laboratory data, in non-linear scale. For these cases we will describe these data with geometric mean. Heterogeneity between sites will be analyzed.

Assessment of loss to follow-up as random across arms

We will analyze the baseline characteristics between lost and non-lost follow up patients and across arms to ensure that loss to follow up occurs randomly. If we find any significant attribute we will adjust the analysis by this/these factors.

Time-to-event data

Time-to-event data (such as time to mortality, time to TB diagnosis or time to treatment initiation (among lab confirmed or all TB)) will be presented using Kaplan-Meier curves with a log rank test (two-sided 0.05 significance level). The analysis of covariates on time-to-event data will be performed using a Hazard Ratios estimated through Cox regression models.

Comparisons between control and intervention arm will be established at prespecified time points (day 7, day 14, day 28 and day 56). Mean time (and SD) to event per study arm will also be estimated.

Significance levels

The significance level for most comparisons is $p=0.05$. For selected secondary endpoints measured at several timepoints and subgroup analysis, the significance level will be $p=0.01$

Study discontinuations & patient disposition

Patient disposition and reasons for premature discontinuations and their frequencies will be tabulated.

Datasets analyzed

Number of patients in each analysis set will be tabulated and listings of any patients excluded from any analysis set will be provided.

Efficacy analysis

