### 3.4 Endpoints

All study endpoints will be compared between control and intervention arm. Also, the final results will be presented disaggregated by sex.

3.4.1 The **primary endpoint** is the proportion of participants diagnosed with microbiologically confirmed TB and started on TB treatment within 72 hours of enrolment\* in whom TB is microbiologically confirmed\*/\*\*

\* The numerator of the primary endpoint includes participants per study arm who are diagnosed with microbiologically confirmed TB and initiated TB treatment within 72 hrs of enrolment. The denominator is the number of enrolled participants in each study arm.

\*\* Participants are defined to have microbiologically confirmed TB if at least one confirmatory TB test (Ultra, AlereLAM) gives a positive result.

**Secondary endpoints** are:

Related to main objective

3.4.2.1 Time-to-TB-treatment-initiation among microbiologically confirmed cases and among all TB cases since enrolment. We will estimate Kaplan Meier curves and hazard ratios at day 7, 14, 28 and 56. Additionally we will compare the time to related estimates (median and IQR) of intervention and control group.

3.4.2.2 Proportion of cases re-admitted to hospital. The numerator will be the number of admissions for any reason (not included in the exclusion criteria) after initial discharge and within 8 weeks from enrolment. The denominator will be the number of participants enrolled.

---

3.4.2.3 Proportion of participants who are diagnosed with TB (irrespective of bacteriological confirmation) and have started on TB treatment within 72 hours of enrolment.

3.4.2.4 Proportion of participants who are diagnosed with microbiologically confirmed TB and are started on treatment at 7, 14 days and 8 weeks of enrolment.

3.4.2.5 Time to laboratory confirmed TB diagnosis and any TB diagnosis since enrolment.

3.4.2.6 Proportion of microbiologically confirmed TB participants started on treatment without Rif resistance information (only AlereLAM positive)).

Related to secondary objectives.

3.4.2.7 Eight-week all-cause mortality. The numerator will be the number of deaths during eight weeks after enrolment, the denominator the number of participants enrolled.

3.4.2.8 In hospital and 4-week all-cause mortality among all participants enrolled (assessed as the eight-week all-cause mortality).

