## 8 Efficacy Analyses

### 8.1 Primary Efficacy Analysis

The primary efficacy is defined as the difference in the proportion of microbiologically confirmed TB and therapy initiated within 72 hours from enrolment in the intervention and control arm. (the comparison by estimating the difference of proportions and see whether is significantly differs from zero)

We will compare the difference of proportions, defined above, between both study arms and see if the results are significantly different from zero. We will test this differences using the test statistics  $z$  has an asymptotic standard normal distribution, and the p-value will be computed as:

$p = 2 \{1 - \Phi(|z|)\}$  where  $\Phi(\cdot)$  is the cdf of a standard normal distribution and  $|z|$  is an absolute value of  $z$ . We will calculate logit-transformed 95% confidence intervals

We will compare this proportion as a risk difference and we will stratify by study countries, baseline CD4 counts (under the hypothesis the highest difference in % of bac confirmed participants between control and intervention arm will occur in those immunosuppressed ones, or in countries with highest % of immunosuppressed admitted participants).

We will evaluate the primary efficacy analysis by ITT and Per protocol populations. We will show the both results in the final analysis document with the correspondent tables and graphs.

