### 8.2 Secondary Efficacy Analyses

All secondary efficacy analyses will be calculated on ITT and Per protocol populations. The Secondary Efficacy Analyses are:

8.2.1 We will compare the proportion of deaths during eight weeks after enrolment between all participants enrolled in two study groups. We will test this differences using the test statistics  $z$  has an asymptotic standard normal distribution. These groups are microbiologically confirmed TB and therapy initiated within 72 hours from admission (numerator/success) and non-lab-confirmed TB or therapy not initiated within 72 hours (denominator/failure). We will compare, using Chi-square test or Fisher Test, these proportion values between intervention and control group.

8.2.2 We will estimate the Kaplan Meier curves to assess time to TB treatment initiation among those with microbiologically confirmed TB and among all TB (also including clinically diagnosed). We will compare both arms using the log rank test. We will use the KM procedure to calculate the survival rate from the survival function. If deemed necessary, to study the effects of some covariates and start of treatment over time we will use the Cox regression.

8.2.3 We will compare the proportion of cases re-admitted to hospital, to test this proportion we calculate the number of admissions after initial discharge and within 8 weeks from enrolment from all participants enrolled. We will compare, using Chi-square test or Fisher Test, these proportion values between intervention and control group.

8.2.4 We will compare the proportion of participants who are diagnosed with TB (irrespective of bacteriological confirmation and are started on TB treatment within 72 hours of enrolment). We will compare, using Chi-square test or Fisher Test, these proportion values between intervention and control group.

8.2.5 We will calculate the proportion of participants who are diagnosed with microbiologically confirmed TB and are started on TB treatment at 7d, 14d, 4 and 8 weeks of enrolment. We will compare, using Chi-square test or Fisher Test, these proportion values between intervention and control group.

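### SAP Table 3 gives between-arm p-values for time to TB treatment separately among starts up to 72 h and after 72 h; these are not randomised comparisons and can mislead, so the rows should be descriptive

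*SAP*

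**What the plan says.** Table 3 in SAP section 13 reports treatment initiation by arm, for ITT and for per protocol. Beneath the row for starting within 72 hours come two rows on timing, "Hours to start treatment (treatments <= 72h") and "Days to start treatment (treatments > 72h"). Each has a p-value cell under both analysis sets. The placeholders in these rows are a count with a percentage, which cannot hold a time. Nothing in the SAP labels the rows descriptive. The SAP names no test for them, but protocol 13.2.2 says that "continuous comparisons will be tested by Student t-test, Anova test or Kruskal Wallis test".

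SAP 8.1 defines the primary effect as the "difference in the proportion of microbiologically confirmed TB and therapy initiated within 72 hours from enrolment" in the two arms, and SAP 3.4 adds that "The denominator is the number of enrolled participants in each study arm". Time to treatment also has an analysis that does not split at 72 h. SAP 8.2.2 reads "We will estimate the Kaplan Meier curves to assess time to TB treatment initiation among those with microbiologically confirmed TB", continues with all TB cases, and compares the arms by log-rank test.

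**The concern.** Which row a participant falls into is decided after randomisation, by when treatment starts, and the strategy is intended to change exactly that. The p-value in each row therefore compares selected subgroups. The ITT column heading does not fit either, because SAP 6.1 defines ITT as all randomised participants and these rows hold only starters in one time band.

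The selection can point the wrong way. A start moved from day 5 to hour 60 joins the early row as one of its slowest members and leaves the late row as one of its fastest, so both averages rise although that patient gained. New cases can lengthen the early row too. Protocol section 12 says "AlereLAM results should be available within two hours from specimen collection. Ultra results should be provided within 24 hours" of collection, so a case found only by urine or stool Ultra may start later than one found by AlereLAM. A reader could then see more patients started within 72 h and, directly below, p-values suggesting slower treatment.

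**Working it through.** **1. The plan's own figure.** Table 3 is an empty shell, so the only stated figure to reproduce is the sample size. With 19% and 26%, two-sided alpha 0.05, 80% power and pooled variance: n = [1.960 × √(2 × 0.225 × 0.775) + 0.842 × √(0.19 × 0.81 + 0.26 × 0.74)]² / 0.07² = 558 per arm. Adding 5% gives 558 × 1.05 = 586, as stated.

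**2. A constructed example at that size.** The start times and total starts are assumed. The 19% and 26%, which the SAP gives for confirmation, are borrowed as the proportions starting by 72 h. Control has 180 starts among 586: 111 spread evenly over 4-72 h (mean 38.0 h) and 69 spread evenly over 73-336 h (mean 204.5 h, or 8.5 days). The intervention does one thing: the 41 earliest late starts move to 48-72 h (mean 60 h). Nobody starts later.
- ≤72 h row: the mean goes from 38.0 h to (111 × 38 + 41 × 60)/152 = 43.9 h and the median from 38.0 to 49.2 h. Kruskal-Wallis p = 0.016, t-test p = 0.018.
- >72 h row: the 28 remaining starts are the latest ones. The median goes from 8.5 to 11.8 days, p < 0.00001.
- All starters: the mean falls from 101.8 to 81.2 h.
- All randomised: 111/586 (18.9%) against 152/586 (25.9%), z = 2.87, p = 0.004 in favour of the intervention. Log-rank censored at 72 h: p = 0.007.

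The first-row result depends on where the moved starts land: p = 0.002 for 60-72 h, 0.08 for 36-72 h, 0.28 for 24-72 h. The second row stays below 0.00001.

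**3. How often it would happen.** Simulation assumptions, none from the documents except 586 per arm: 25% of controls ever start; 65% of starts are by 72 h (gamma, mean about 29 h); late starts fall at 72 h plus an exponential with mean 6 days; Mann-Whitney test at 0.05. Expected control counts are 586 × 0.25 × 0.65 = 95.2 early and 586 × 0.25 × 0.35 = 51.3 late starts.

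If starts due at 72-144 h move to 48-72 h, 51.3 × (1 − e^(−72/144)) = 20.2 starts move. Started by 72 h: 95.2/586 = 16% becomes 115.4/586 = 20%. Early mean: (95.2 × 28.6 + 20.2 × 60)/115.4 = 34.1 h, against 28.6 h. Late mean: 72 + 144 = 216 h (9.0 days) becomes 144 + 144 = 288 h (12.0 days).

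If instead 3 or 6 points of new cases (17.6 or 35.2 participants) start at 36-72 h (mean 54 h), the early mean rises to about 32.6 or 35.4 h. If they start at 24-48 h (mean 36 h), it rises to about 29.8 or 30.6 h.

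Share of simulated trials with the intervention significantly slower:

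| Scenario | ≤72 h row | >72 h row | Both rows |
|---|---|---|---|
| Starts due at 72-144 h moved to 48-72 h | about 50% | about 87% | about 44% |
| Only starts due at 72-108 h moved to 48-72 h | about 22% | about 44% | about 10% |
| 70% of starts due at 72-144 h moved to 24-72 h | not reported | not reported | about 8% |
| 3-6 points of new cases at 36-72 h | 35-79% | chance (2-3%) | not reported |
| 3-6 points of new cases at 24-48 h | 11-28% | chance (2-3%) | not reported |
| Random 40% of late starts given ordinary early times (16% to 20% by 72 h) | 2-3% | 2-3% | 0% |
| Every start shortened by 30% | 0% | 0% | 0% |
| No effect | 2-3% | 2-3% | not reported |

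**The case against.** No decision in the SAP rests on these rows. The primary test uses all enrolled participants, SAP 8.2.2 does not split at 72 h, proportions started are compared at 72 h (8.2.4) and at later times (8.2.5), and SAP 6.3 reserves inference for the primary objective. No analysis in SAP section 8 mentions the two rows, and their unsuitable placeholders suggest an unfinished template. The pattern in both rows also needs moved starts to land just under 72 h. The protocol gives a reason to expect otherwise: its background section says that waiting for CD4 counts or a severity assessment may delay AlereLAM, and universal testing removes that wait. Samples are aimed for within 24 h of enrolment and Ultra results within 24 h of collection, so 36-72 h for new cases is a choice, not a documented figure.

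Most of this stands, and it limits the size of the point. It does not make the p-values valid: the shell prints them, nothing marks them descriptive, and they have no randomised interpretation in either direction. SAP 8.2.2 does not fully replace them, since it too is restricted to TB cases.

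A reader might infer that the more starts the intervention brings under 72 h, the stronger the distortion. That does not follow: the same gain from 16% to 20% gives chance-level results when moved starts take ordinary early times. Nor do the rows split on the full primary outcome. They take all starts, confirmed or not, and so use only its timing component.

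**Conclusion.** The point holds as a minor, table-level correction. The four p-values (two rows, two analysis sets) compare groups selected by timing after randomisation and can be significant against an intervention that delays nobody. Whether they would be depends on where moved or added starts land. The rates above run from chance level or below to about 44% for both rows together, and up to about 87% for a single row. They rest on assumed start times and an assumed number of starters, because the documents give neither. New cases affect only the early row. A reader might go further and infer that the primary result or the planned time-to-treatment analysis is distorted by this split; the documents do not support that, because neither uses it.

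**What to change.** In Table 3, delete the p-values from the rows "Hours to start treatment (treatments <= 72h") and "Days to start treatment (treatments > 72h"), under both ITT and per protocol. Replace the count-and-percentage placeholder with median (IQR), and label both rows as descriptive, among starters only, and not a between-arm comparison. Add a note sending readers to the comparisons of proportions started among all randomised participants: 72 h (SAP 8.1, 8.2.4 and Table 4), 7 and 14 days (SAP 8.2.5), and 48 h, which the protocol synopsis lists as a sub-analysis of the primary endpoint and the SAP should carry over. Table 4 already has a risk difference with 95% CI at 72 h; give the same at the other times beside the planned chi-square or Fisher tests. The cost is an edit to the table shell. No new data are needed, and all that is lost is the p-values in two rows.
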